### 8.1.7 Analysis

A general summary table reporting the number and percentage of subjects, and the number of events will be provided. The following categories will be included in the summary table:

- Subjects with at least one TEAE
- Subjects with at least one serious TEAE
- Subjects with at least one severe TEAE
- Subjects with at least one TEAE leading to death
- Subjects with at least one TEAE for which the study drug was interrupted
- Subjects with at least one TEAE for which the study drug was withdrawn
- Subjects with at least one TEAE that was considered treatment-related
- Subjects with at least one serious TEAE that was considered treatment-related
- Subjects with at least one TEAE that was considered related to study procedure

A treatment-emergent analysis of AEs will be done. Frequency of subjects presenting with AEs, non-serious AEs, AEs leading to study drug withdrawal, AEs by maximum severity, related AEs by study drug relationship, AEs related to study procedures and SAEs will be tabulated for each treatment group by system organ class and preferred term.

The tables by system organ class and preferred term are sorted by decreasing frequency of SOC and PT (overall). If more than one SOC or PT have the same frequency, then the corresponding SOC and PT are sorted alphabetically.

A detailed list of Tables and Listings can be found in section 16.4 and section 18.3, respectively.

### 8.1.8 Subgroup analysis

The frequency of subjects with TEAEs will be provided by system organ class and preferred term for the subgroups defined in Section 7.4. These summaries will be sorted alphabetically by SOC and PT.

## 8.2 Laboratory Evaluations

### 8.2.1 Available data

The following tests will be included in the clinical laboratory analysis:

ALX0171-C201 – Statistical Analysis Plan – final 1.0 –  
31AUG2018 Page 28/92

- Clinical biochemistry: alanine aminotransferase, aspartate aminotransferase, creatinine, sodium, potassium, chloride, C-reactive protein,  $\gamma$ -glutamyl-transferase, blood urea nitrogen
- Hematology: hemoglobin, hematocrit, red blood cell count and indices, mean corpuscular hemoglobin, mean corpuscular hemoglobin concentration, platelet count (or estimate), white blood cell count including differential (lymphocytes, neutrophils, monocytes, basophils and eosinophils)

### 8.2.2 Laboratory units

The statistical analysis will only present results in Standard International (SI) units.

### 8.2.3 Abnormalities

All values will be compared to their matching normal ranges. The classification available in the standard data tabulation method (SDTM) dataset will not be used for the statistical analysis. The classification will be re-calculated in the analysis data model (ADaM) dataset by using the values and normal ranges in SI units. (See Section 14.3.2.2 for more details on abnormality classification).

### 8.2.4 Worst-case abnormality

The worst-case abnormality is derived for each parameter separately.

All non-missing post-baseline values (including unscheduled measurements and follow-up measurements) will be used to derive the worst-case. (see Section 14.3.2.3 for more details on worst-case abnormality classification).

### 8.2.5 Analysis

For laboratory parameters, descriptive statistics will be computed on the actual values and the change from baseline to Day 14 for each parameter according to general rules (see Section 5.4.1). In addition, all laboratory values will be categorized according to their normal ranges as abnormal low, normal or abnormal high. A shift table of worst post-baseline category versus baseline category will be created.

A detailed list of Tables and Listings can be found in section 16.5 and section 18.5, respectively.

## 8.3 Physical Examination

Abnormal findings in physical examinations (including heart auscultation, examination of abdomen, skin and ear/nose/throat) will be listed (see Section 16.4).

## 8.4 Vital Signs

The available parameters are: heart rate and weight. The actual values, change from baseline and percent change from baseline will be summarized over time using descriptive statistics (see Section 5.4.1). Heart rate will also be presented graphically in mean  $\pm$  SE Plot (excluding the in-hospital post-treatment timepoints).

A detailed list of tables, listings and figures can be found in Section 16.6, Section 18.6 and Section 17.5, respectively.

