- Peripheral capillary O2 saturation (SpO2)
- Vital signs: body weight, body temperature, heart rate, respiratory rate
- Clinical laboratory test results:
  - Clinical chemistry: alanine aminotransferase, aspartate aminotransferase, creatinine, sodium, potassium, chloride, C-reactive protein,  $\gamma$ -glutamyl-transferase, blood urea nitrogen
  - Hematology: hemoglobin, hematocrit, red blood cell count and indices, mean corpuscular hemoglobin, mean corpuscular hemoglobin concentration, platelet count (or estimate), white blood cell count including differential (lymphocytes, neutrophils, monocytes, basophils, eosinophils).

Safety lab assessments are planned two times during the study (at screening and at the FU visit) and will be performed by the local laboratory in order to allow timely availability of the results.

**Clinical Activity** Outcome Measures‡

- Heart rate and SpO2
- Feeding: type of feeding support, and (time and date of) sufficient feeding to enable hospital discharge, in the opinion of the Investigator (with particular attention to hydration and breathing comfort during feeding)
- Respiratory rate measured over a 1-minute interval
- Wheezing as assessed during lung auscultation
- Cough during the night and during the day
- Respiratory muscle retractions (supraclavicular, intercostal, and subcostal)
- General appearance: activity, irritation, and responsiveness
- Body temperature

Based on the Clinical Activity Outcome Measures, composite scores such as the Respiratory Distress Assessment Instrument (RDAI) score (based on wheezing and respiratory muscle retractions), Respiratory Assessment Change Score (RACS; based on RDAI and change in respiratory rate), and a Global Severity Score (based on respiratory parameters, medical interventions, feeding, general appearance and body temperature) will be calculated.

The feeding and oxygen saturation outcome measures will be used to calculate Time to Clinical Response. Subjects will be considered to have met the Clinical Response criteria when both of the following criteria are fulfilled:

- Stable oxygen saturation on room air, defined as SpO2 > 92% over a period of ≥ 4 hours. In case of oxygen supplementation, the level of supplementation is to be considered for reduction at least three times per day. Provided oxygen saturation is stable, attempts to remove the supplementation will be done at least three times a day.

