### **3.6.7. EVALUATION OF SAFETY PARAMETERS**

The IDMC will evaluate the cumulative safety data after completion of each safety cohort, and periodically during the parallel dose ranging phase of the study (see section 3.1.1). Further details will be provided in the IDMC charter.

All safety analyses will be performed using the Safety Population.

AEs will be fully described and coded according to the Medical Dictionary for regulatory Activities (MedDRA). A treatment-emergent analysis of AEs will be done. Frequency of subjects presenting with AEs, AEs leading to withdrawal, adverse drug reactions, and SAEs will be tabulated for each treatment group by system organ class and preferred term.

For laboratory parameters, descriptive statistics (mean, median, standard deviation, minimum, and maximum) will be computed on the actual values and the change from baseline for each parameter. All laboratory values will be categorized according to their normal ranges as below, within or above normal.

Other safety variables, including e.g., heart rate and SpO2 levels, need for O2 therapy (and when applicable, relevant parameters such as duration of O2 therapy needed, oxygen delivery mode, flow of inspired oxygen), or any significant worsening requiring immediate or intensive medical intervention, will be fully depicted using descriptive statistics. Where relevant, actual values and changes from baseline, and/or and shift tables according to normal ranges, will be included.

Findings in physical examinations will be listed.

Body height, body weight, and body temperature results will be summarized by descriptive statistics.

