### 4.3.3 Other Endpoints

- Evolution over time in clinical symptoms (SpO2, feeding, respiratory rate, wheezing, cough, respiratory muscle retractions, and general appearance)
- Evolution over time in RDAI, RACS
- Length of hospital stay defined as time between admission and discharge
- Length of hospital stay for RSV defined as time between admission and discharge excluding prolongation due to SAE other than RSV worsening
- Time between first study drug administration and discharge
- Duration of severe disease, defined as time from admission to hospital to time of clinical response
- Duration of supplemental oxygen therapy
- Duration of feeding support
- Initiation of invasive and non-invasive ventilation and duration of respiratory support
- Transfer to ICU and duration of ICU stay
- Parent(s)/Caregiver(s) assessment of the clinical condition of the subject
- Evolution of serum biomarker over time

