## 7.2.2 Other Secondary Endpoints

### 7.2.2.1 Clinical Response

Clinical response is defined as achieving adequate oxygen saturation and adequate oral feeding. The time to clinical response (hours), defined as the time between the first study drug administration and achieving clinical response, will be summarized using KM estimates and presented graphically. Subjects who already achieved clinical response before the start of dosing, will be excluded from the analysis.

The time to achieving adequate oxygen saturation and the time to achieving adequate oral feeding will be summarized similarly. Subjects who already achieved adequate oxygen saturation or already achieved adequate oral feeding before the start of dosing, will be excluded from the analysis, respectively.

The time to event for subjects with missing data and/or who did not reach the clinical response for oxygen saturation and oral feeding during the trial will be censored at the last nonmissing assessment of blood oxygen level in the vital signs domain (VSTESTCD=OXYSAT) or assessment of adequate oral feeding (DCTESTCD=FEDADQ) If only one condition is reached, then the time to clinical response is censored at the last non missing assessment of the condition which was not met. The same rule will be applied for the time to achieving adequate oxygen saturation and the time to achieving adequate oral feeding.

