## 7.3 Other Efficacy Analyses

- Evolution over time in clinical symptoms will be evaluated. The body temperature and respiratory rate (actual values, change from baseline and percent change from baseline) will be summarized descriptively over time. Frequency tabulations will be provided to summarize the feeding, respiratory distress parameters (Wheezing (during inspiration/expiration), lung fields affected, crackles/crepitations, respiratory muscle retractorations (supravascular, intercostal and subcostal) , cough and general appearance of the subject over time. Respiratory rate and body temperature will also be presented graphically in mean  $\pm$  SE plots (excluding the in-hospital post-treatment timepoints).
- Respiratory Distress Assessment Instrument (RDAI) and Respiratory Change Score (RACS) will be calculated (see Section 14.2.3 and 14.2.4 for calculation method, respectively) . Actual values (RDAI, RACS) and changes from baseline (RDAI) will be summarized over time using descriptive statistics (both subitem and totals). RDAI, change from baseline in RDAI and RACS will also be presented graphically in mean  $\pm$  SE plots (excluding the in-hospital post-treatment timepoints). Similar to GSS, bar charts will be generated for RDAI to visualize contributing subitems.
- Length of hospital stay (in days – see section 14.2.9 for calculation method) defined as time between admission and discharge for the initial hospitalization will be summarized as descriptive statistics and using KM estimates. In case of missing discharge information the subject will be censored on date(time) of trial termination.
- The time between first study drug administration and discharge (in days) for the initial hospitalization will be summarized as descriptive statistics and using KM estimates. In case of missing discharge information the subject will be censored on date(time) of trial termination.

- Length of hospital stay for RSV: The time between hospital admission and discharge (in days) excluding prolongation due to SAE other than RSV worsening. Time will be summarized as descriptive statistics and using KM estimates. In case of missing discharge information the subject will be censored on date(time) of trial termination. If needed time will be imputed with 18u00 (see section 14.2.10 for calculation details).

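### The SAP plans no summary of measured SpO2 by timepoint and arm, although the protocol commits to one and both documents list SpO2 over time as an endpoint

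*SAP*

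**What the plan says.** The protocol treats SpO2 as both a safety and an activity measure. Its Synopsis lists it among the safety outcome measures. Section 3.6.7 takes up "Other safety variables, including e.g., heart rate and SpO 2 levels", together with oxygen need, and says these variables "will be fully depicted using descriptive statistics", with changes from baseline where relevant. Protocol 3.6.4 and SAP 4.3.3 both include SpO2, in first place, in the endpoint "Evolution over time in clinical symptoms".

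The SAP splits these measurements between two sections. On vital signs, SAP 8.4 states: "The available parameters are: heart rate and weight". On clinical symptoms, SAP 7.3 states: "The body temperature and respiratory rate (actual values, change from baseline and percent change from baseline) will be summarized descriptively over time". It then adds frequency tables for feeding, respiratory distress signs, cough and general appearance. Neither section mentions SpO2 values.

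Elsewhere, SAP 7.2.2.1 censors time to clinical response using "blood oxygen level in the vital signs domain (VSTESTCD=OXYSAT". The SAP itself therefore places SpO2 in the vital signs data.

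**The concern.** An analyst who follows the SAP exactly will produce no table or figure of SpO2 level, or of change in SpO2, for any arm at any post-dose timepoint. A listed endpoint is left without its analysis, and a protocol commitment on safety is dropped without being recorded as a change.

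The variable is relevant in this trial. Safety is part of the primary objective. Protocol 1.3.3 names airway hyperresponsiveness as a potential risk and reports bronchoconstriction in 10 of 24 adults with hyperresponsive airways (42%). It also explains that the salbutamol given before each dose in the earlier infant study is no longer required, and it promises close monitoring of this risk across the whole study. Oxygen saturation at fixed times after nebulisation, by dose, is one of the descriptions a reader of the study report would expect.

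**Working it through.** The plan gives no figure to reproduce here. The check is to trace SpO2 from commitment to output.

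**1. Commitments.** The Protocol Synopsis (safety outcome measures), Protocol 3.6.7, Protocol 3.6.4 and SAP 4.3.3 all name SpO2.

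**2. Collection.** The Schedule of Assessments (Protocol, and SAP 19.1.3 for version 3.0) places SpO2 before each dose and at these post-dose times in the treatment period: Day 1 at 2 h and 5 h, Day 2 at 2 h and 5 h, Day 3 at 2 h.

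- Post-dose readings per infant: 2 + 2 + 1 = 5.
- Planned maximum over about 180 infants: 5 × 180 = 900.

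This counts planned readings, not expected data. Missed visits and discontinuations lower it. It leaves out the morning and evening in-hospital readings after treatment, and the Day 3 5 h reading that applied only at German sites under version 1.0.

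**3. Outputs, item by item for the symptom endpoint.**

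- Respiratory rate: Tables 14.2.4.1 and 14.2.4.2, Figures 14.2.4.1 and 14.2.4.2.
- Feeding: Table 14.2.4.5.
- Wheezing and retractions: Table 14.2.4.6.
- Cough: Table 14.2.4.7.
- General appearance: Table 14.2.4.8.
- SpO2: none.

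**4. Outputs on the safety side.** Protocol 3.6.7 names heart rate and SpO2 together. Heart rate is covered by Tables 14.3.3.1 and 14.3.3.2 and Figures 14.5.1.1 and 14.5.1.2. The two tables are described as being per test, but SAP 8.4 limits the tests to heart rate and weight. SpO2 is not included.

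**5. Declared changes.** SAP 13 records the added Cox model, the added endpoints and the added subgroup analyses. It does not mention dropping SpO2.

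**6. What the indirect route can show.** SAP 7.2.2.1 summarises time from first dose to adequate oxygen saturation by Kaplan-Meier, in Table 14.2.2.1 and, by treatment group, Figure 14.2.2.2. Protocol 3.4.4.1 defines adequacy as SpO2 above 92% on room air for at least 4 hours. Infants who met this before dosing are excluded, and each remaining infant contributes only the first time of success. The analysis therefore gives no SpO2 level at 2 h or 5 h, and no information on readings after first attainment.

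**The case against.** The strongest reply is that oxygenation after dosing is far from ignored. Time to adequate saturation starts at first dose and is shown by arm. Saturation also feeds time to clinical response and duration of severe disease. Oxygen use is cross-tabulated against baseline by treatment group, and its duration from first dose is summarised (Tables 14.2.6.6 and 14.2.6.4). The medical-interventions item of the Global Severity Score scores conventional oxygen. Protocol 3.4.4.3 requires clinically significant oximetry findings to be recorded as adverse events, which are tabulated by arm. All of this stands. A reader might infer that the SAP never uses SpO2, or never sets post-dose oxygenation side by side between arms; the documents contradict both.

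A reader might also infer that a brief fall after inhalation would go unseen only because this table is missing. That is not supported either. The first scheduled reading is 2 h (±0.5 h) after the end of the second nebulisation, so a short fall could be missed there too. Until the oxygen criterion is met, continuous monitoring with adverse event reporting is better placed to catch one. Wheezing, retractions and respiratory rate, also scheduled at 2 h and 5 h, are summarised over time. Nothing in the documents makes SpO2 the single best marker of bronchoconstriction.

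The wording of SAP 8.4 can be read as setting the scope of that section, not as denying that SpO2 was collected. Temperature and respiratory rate are also absent there because SAP 7.3 handles them. That is fair, but SAP 7.3 does not handle SpO2.

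Finally, oxygen is started and weaned by local practice, so a raw mean SpO2 by arm mixes supplemented and room-air infants. This is a reason to present the data carefully. It does not justify omitting them without saying so.

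The indirect outputs do not replace the missing one. Adverse event capture depends on a judgement of clinical significance, oxygen duration reflects treatment given, and the full vital signs listing (16.2.6.1) is not a summary by arm.

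**Conclusion.** The point holds in a limited form. Measured SpO2, as actual values or change from baseline, has no planned summary by timepoint and arm. The protocol promises a description of SpO2 levels, and both documents list their course over time as an endpoint. The omission is undeclared, and SAP 8.4 does not fit with SAP 7.2.2.1, which places oxygen saturation in the vital signs domain.

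The size is one item of one endpoint in the Other category plus one protocol-named safety variable, with five scheduled post-dose readings per infant in the treatment period. No primary or key secondary test, error rate or power figure is touched. It should be corrected because following the SAP literally leaves committed work undone, not because a safety signal is known to be hidden.

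The conclusion assumes that SAP 8.4 governs what enters Tables 14.3.3.1 and 14.3.3.2. If those tables were programmed to include every test in the vital signs domain, much of the gap would close, but the text would still need to say so.

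**What to change.** - Add SpO2 (OXYSAT) to the parameters in SAP 8.4, and cross-reference it in SAP 7.3 so that the symptom endpoint of SAP 4.3.3 is complete.
- Add it to Tables 14.3.3.1 and 14.3.3.2 and to the mean (SE) figures, by scheduled timepoint and arm. Show the actual value, the change from baseline as defined in SAP 5.3.1, and the change from the same day's pre-dose reading. The last is needed because the SAP baseline precedes the first dose only.
- Present each timepoint with, or split by, supplemental-oxygen status. Protocol 3.4.4.3 has oxygen flow and method captured with the SpO2 values.
- Apply any count at or below 92% to room-air readings only, since the protocol's response criterion is defined on room air.
- If the sponsor prefers not to summarise SpO2, declare and justify that in SAP 13.

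The cost is SAP wording plus a few descriptive table rows and figures. No new data, tests or multiplicity adjustment are needed.

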## 9 ANALYSIS OF PHARMACOKINETICS

See section 7.2.2.3 for details

## 10 ANALYSIS OF PHARMACODYNAMICS

Individual subject serum biomarker concentrations (KL-6) and collection times will be listed.

Biomarker results will be summarized as continuous variables by treatment and time point. Changes from baseline and percent changes from baseline will also be summarized (see Section 5.4.1 for more details) These summary statistics will also include the number and percentage of subjects with serum KL-6 levels that are below the lower limit of quantification (LLOQ) by treatment and time point. For the summary statistics, samples that are below the lower limit of quantification (LLOQ) will be assigned to the value of the LLOQ level. Biomarker results (actual values and change from baseline) will also be presented graphically in mean (arithmetic)  $\pm$  SE plots. In the listing the imputed values will be flagged and the LLOQ level will be reported in a footnote. The analysis will be performed on both mITT and RSV infected population

A detailed list of Tables and Listings can be found in section 16.7 and section 18.7, respectively.

## 11 IMMUNOGENICITY ANALYSIS

Immunogenicity will be assessed through summary tables and figures, and listing of individual results by subject.

A detailed list of tables, listings and figures can be found in Section 16.8, Section 18.9 and Section 17.7, respectively.

### 11.1 Available data

#### 11.1.1 ADA

Immunogenicity of ALX-0171 was monitored in all clinical studies using MSD-based homogeneous bridging ADA assays via a tiered approach. In a first step, samples are evaluated in a screening assay and are scored possibly ADA positive based on the screening

cut-point (SCP), allowing a 5% false positivity rate. Positively screened samples are subsequently analyzed in a confirmation assay, which is a drug displacement assay to confirm the specificity of the ADA screening result. All positively confirmed samples are subsequently analyzed in an end-point titration assay to determine the antibody titer. The  $\log_{10}(\text{titer})$  will be reported. The titer represents the last dilution factor of the sample's titration series still scoring positive in the ADA assay. Samples scoring negative in the ADA assay are not titrated and the respective  $\log_{10}(\text{titer})$  is reported as  $<\log_{10}(\text{Minimal required dilution [MRD]})$  with  $\text{MRD}=24$ , i.e.  $\log_{10}(\text{titer}) < 1.38$ . The latter negative samples are not included in descriptive statistics on titers.

For each subject, immunogenicity results will be categorised based on the presence of pre-existing antibodies (pre-Ab) and the presence of treatment-emergent (TE) ADA, as shown below. Classification is performed by the Bioanalytical laboratory (Ablynx GLP-Pharma) performing the ADA sample analysis and they report both  $\log_{10}(\text{titer})$  and subject classification.

Subjects will be classified based on the pre-Ab and TE ADA status (subject classifications):

1. Pre-Ab NEG – TE ADA NEG
2. Pre-Ab NEG – TE ADA POS
3. Pre-Ab POS – TE ADA NEG
4. Pre-Ab POS – TE ADA POS
5. Pre-Ab POS – TE ADA EQ
6. TE ADA inconclusive: Pre-Ab NEG – Post-dose missing
7. TE ADA inconclusive: Pre-Ab POS – Post-dose missing
8. TE ADA inconclusive: Pre-dose missing – Post-dose NEG
9. TE ADA inconclusive: Pre-dose missing – Post-dose POS

Note: Subject classification 'Inconclusive TE ADA' (that is generally used in case drug tolerance is exceeded) is not included here since drug washout samples are available for ADA testing.

Below subject categories are only to be used in the tables and figures on incidence and subgroup analysis (for all other figures and tables subject classifications are used as described above).

Possible subject categories:

1. Pre-Ab NEG – TE ADA NEG
2. Pre-Ab NEG – TE ADA POS
3. Pre-Ab POS – TE ADA NEG
4. Pre-Ab POS – TE ADA POS
5. Pre-Ab POS – TE ADA EQ
6. TE ADA inconclusive: Pre-Ab NEG – Post-dose missing
7. TE ADA inconclusive: Pre-Ab POS – Post-dose missing
8. TE ADA inconclusive: Pre-dose missing – Post-dose NEG
9. TE ADA inconclusive: Pre-dose missing – Post-dose POS

10. Total Pre-Ab NEG (“Pre-Ab NEG – TE ADA NEG”, “Pre-Ab NEG – TE ADA POS” and “Pre-Ab NEG – Post-dose missing”)
11. Total Pre-Ab POS (“Pre-Ab POS – TE ADA NEG”, Pre-Ab POS – TE ADA POS”, “Pre-Ab POS – TE ADA EQ” and Pre-Ab POS – Post-dose missing”)
12. Total TE ADA NEG (“Pre-Ab NEG – TE ADA NEG” and “Pre-Ab POS – TE ADA NEG”)
13. Total TE ADA POS (“Pre-Ab NEG – TE ADA POS” and “Pre-Ab POS – TE ADA POS”)
14. TE ADA POS within Pre-Ab NEG
15. TE ADA POS within Pre-Ab POS

